3.2.1.14 Sample size and power calculation

The sample size calculation is based on the following assumptions: two-sided alpha level of 0.05 and power of 0.80. The study group decided that the ability to detect an effect size of 0.5 standard units at the total score at the WHO Organization's questionnaire on the attitudes towards people with psychosocial disabilities as rights-holders between the two groups would be worth finding. The unit of randomization will be the hospital units. The 28 hospitals unit clusters will be randomized with a 1:1 allocation ratio to the intervention or control arm. Based on data from previous cRCT in Ghana [182, 183], we assume a 20% loss to follow-up and ICC=0.05. Based on these assumptions, we calculated that 126 participants would be required in each arm group.

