Since the data are continuous and longitudinal, linear mixed-effects (LME) regression models will be used to estimate average intervention effects while considering the shared variance of repeated measures and the clustered variance. Correlations arising from repeated measures will be accounted for by specifying an autoregressive covariance structure. Each outcome will be analyzed separately using LME. Time, intervention arm, and their interaction will be included in the model as fixed effects, while participants will be evaluated as random effects. Time will be entered as a categorical variable with levels corresponding to post-training and 3 AND 6 months. The effect of the intervention on the outcomes will be captured by the interaction between intervention and time, which will assess the mean difference between the intervention arms (QR e-training vs. control) in changes of outcomes over time within each group. Effect sizes will be reported as mean differences for each time point and intervention arm, with 95% confidence intervals.

(Random intercept with two group-level covariates and interaction).

Level 1:

$$Y_{ij} = b_{0j} + \varepsilon_{ij}$$

Level 2:

$$b_{0j} = \beta_{00} + \beta_{01}w_j + \beta_{02}t_j + \beta_{03}w_jt_j + b_{0j}^*$$

Combined:

$$Y_{ij} = \beta_{00} + \beta_{01}w_j + \beta_{02}t_j + \beta_{03}w_jt_j + b_{0j}^* + \varepsilon_{ij}$$

- Y_{ij} = attitudes
- β_{00} = "average mean" of units mean attitudes

- b_{0j}^* = difference between specific unit mean attitudes and “average mean” of units mean attitudes
- ε_{ij} = difference between individual attitudes and unit mean attitudes
- t_j = time (3 = at 6 months; 2 = at 3 months; 1 = post – training; 0 baseline)
- w_j = (1 = QR training; 0 control)
- β_{02} = regression coefficient for time
- β_{01} = regression coefficient for unit average attitudes when assigned to QR
- β_{03} = regression coefficient for the interaction of time and intervention

3.1.2.4 Secondary analyses.

Secondary outcomes will be the change in practices and experiences related to substitute-decision making and coercion. The change in practices will be evaluated at three months and six months, while the change in experiences will be evaluated both post-intervention and at three months and six months. These changes will be evaluated using the same methodology already described for the main analyses.

References

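### The primary effect is an unadjusted difference in change, which is valid but less precise than adjusting for the baseline score already collected; stated power is at risk only if baseline and follow-up correlate weakly

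*Protocol*

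**What the plan says.** Section 3.1.2.3 defines both primary outcomes as changes and fixes the mean model: "Time, intervention arm, and their interaction will be included in the model as fixed effects". No baseline score or other covariate is listed. The effect is the interaction, "which will assess the mean difference between the intervention arms (QR e-training vs. control) in changes of outcomes over time within each group". The key to the equation codes time from 0 (baseline) to 3 (6 months). The arm term applies at every time, so the arm means at baseline are left free. The equation carries one random intercept per unit, constant over time, and the text adds an autoregressive structure for the repeated measures. Section 3.1.2.4 applies the same method to the secondary outcomes.

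The sample size in section 3.2.1.14 is set on a different quantity, "an effect size of 0.5 standard units at the total score" of the attitudes questionnaire, with "two-sided alpha level of 0.05 and power of 0.80". It uses no correlation between baseline and follow-up.

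Two design facts in section 3.1.1.3 bear on the remedy. Participants learn their arm only after the baseline assessment. They are recruited after their unit has been randomised, by assistants blind to allocation.

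**The concern.** With a free baseline difference, the interaction at a given visit is the follow-up difference minus the baseline difference. Chance imbalance at baseline is thus removed with a coefficient of 1, however weakly baseline predicts follow-up. Where prediction is weak, this puts baseline noise into the estimate. A regression on baseline would estimate the coefficient instead.

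The stake is the width of the confidence intervals on every primary and secondary outcome, in a trial with only 14 units per arm. There is also a question of power. The variance of a change score depends on the correlation, and the sample size calculation does not consider it.

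**Working it through.** **Inputs.** From section 3.2.1.14: 28 units at 1:1, so 14 per arm; "we assume a 20% loss to follow-up and ICC=0.05"; effect 0.5 SD; two-sided 0.05; 126 per arm. The correlation ρ between a participant's baseline and follow-up scores is not given. I assume a range.

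**The plan's own figure.** The protocol does not show its formula. A follow-up-only comparison of unit means with t on 26 df gets there. The variance with m completers per unit is 2[1 + (m − 1)0.05]/(14m).
- m = 6: 2 × 1.25/84 = 0.0298, power 0.797, just short.
- m = 7: 2 × 1.30/98 = 0.0265, power 0.840.
- 7/0.8 = 8.75, rounded to 9 per unit; 9 × 14 = 126.

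So 126 per arm is reproduced as a sample size for the raw follow-up score. After 20% loss, 126 × 0.8 = 100.8 per arm remain, or 7.2 per unit. The design effect is 1 + 6.2 × 0.05 = 1.31. Follow-up-only power is then 0.873 (normal) or 0.847 (t, 26 df).

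**Variance factors under the written unit intercept.** The variance of the effect is 2 × factor/100.8.
- Difference in change: the constant unit effect cancels, so the factor is 2(1 − ρ).
- Adjusted for baseline, including the unit mean: 1.31 − (ρ + 0.31)²/1.31.
- The ratio of adjusted to change simplifies to (1.62 + ρ)/2.62, which is below 1 for every ρ below 1.

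| ρ (assumed) | Change factor | Adjusted factor | Ratio | Power, change / adjusted (normal) | Power, change / adjusted (t, 26 df) |
|---|---|---|---|---|---|
| 0.1 | 1.80 | 1.182 | 0.66 | 0.754 / 0.904 | 0.721 / 0.882 |
| 0.2 | 1.60 | 1.111 | 0.69 | 0.801 / 0.920 | 0.771 / 0.900 |
| 0.3 | 1.40 | 1.026 | 0.73 | 0.851 / 0.939 | 0.823 / 0.921 |
| 0.4 | 1.20 | 0.925 | 0.77 | 0.900 / 0.958 | 0.877 / 0.944 |
| 0.5 | 1.00 | 0.809 | 0.81 | 0.944 / 0.976 | 0.927 / 0.967 |
| 0.7 | 0.60 | 0.531 | 0.89 | 0.996 / 0.998 | 0.993 / 0.997 |

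The change contrast falls below 0.80 when ρ is under about 0.20 (normal) or 0.26 (t).

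**Autoregressive decay.** I take a generalised least squares model with four equally spaced visits, 7 completers per unit, unit variance 0.05 and no participant variance. The correlation with baseline is 0.05 + 0.95 × a^lag, where a is the autoregressive parameter. Powers use the normal approximation.
- a = 0.5: the correlations are 0.53, 0.29 and 0.17. Power with baseline free is 0.949, 0.834 and 0.775 at the three follow-up visits, against 0.978, 0.931 and 0.908 with a common baseline mean.
- a = 0.6: at 6 months, 0.818 against 0.924.
- a = 0.4 with participant variance 0.2: the 6-month correlation is 0.30, and power is 0.840 against 0.933.

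Only strong decay with no stable participant component takes the 6-month contrast below 0.80 on this basis.

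**The case against.** The strongest reply is that an arm-by-time interaction in a mixed model is a standard, unbiased analysis, and that covariates are often settled in a SAP, which is not at hand. The first part stands: this is a matter of efficiency, not of bias. The second carries less weight, because the protocol itself lists the fixed effects and defines the effect.

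A second reply concerns the remedy. Participants are recruited after units are randomised, so equal baseline means depend on the recruiters' blinding holding. The planned contrast does not assume equal baselines. This stands against a model that imposes a common baseline mean, and is why I put the covariate version first.

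Stronger readings are tempting, but the documents do not support them.
- *The trial is underpowered.* This needs a low correlation, and none is stated. Applying the full design effect of 1.31 to the change score would move the 0.80 threshold up to ρ of 0.39 (normal) or 0.43 (t). That requires unit effects that vary between visits, whereas the equation has one constant unit intercept. The completer-only figures are also somewhat pessimistic, since a mixed model can keep the baseline scores of participants who drop out.
- *A true/false knowledge quiz after training would correlate weakly with baseline, so stated power is missed.* Power is stated only for the attitudes score. None is claimed for knowledge.
- *The baseline score is wasted.* It is used, with a suboptimal weight.

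**Conclusion.** The point holds as a loss of precision. Under the written unit intercept and constant ρ of 0.2 to 0.7, the adjusted variance is 0.69 to 0.89 of the planned one. Confidence intervals would be about 17% to 6% narrower (√0.69 = 0.83; √0.89 = 0.94). The direction of the gain does not depend on ρ; its size does, and ρ is my assumption.

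The risk to the stated 0.80 power is conditional. It arises if ρ is about 0.2 to 0.3 or lower, or at 6 months if the autoregressive correlation decays strongly. At ρ of 0.4 or more under the constant unit intercept, planned power on the attitudes score is at least 0.877.

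One inconsistency in section 3.1.2.3 should be settled at the same time. The prose gives time three levels, all after training, while the equation key adds baseline as level 0. I have followed the key and the reference to changes, which fit the stated purpose of the interaction.

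**What to change.** Model the post-training, 3-month and 6-month scores with fixed effects for visit, arm and their interaction, and with the participant's baseline score as a covariate, preferably also the unit's mean baseline score. Report the adjusted mean difference with its 95% interval at each visit.

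An alternative is a constrained longitudinal model: baseline stays as a response with one mean common to both arms, and arm effects enter only after baseline. If this is chosen, say that it relies on the blinded recruitment described in section 3.1.1.3.

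Use the same approach for the secondary outcomes at their own visits, and make the levels of time agree between the prose and the equation key. The cost is a wording change before unblinding and at most about one degree of freedom per covariate. The baseline scores are already scheduled in Appendix 5, and no participants need to be added.

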3.1.2 Analysis plan

3.1.2.1 Descriptive analyses.

Descriptive analyses will be conducted for the variables of interest (listed above). Univariate analyses will be used to examine continuous variables by assessing the mean, the median, and the spread of the data. Tabular analyses will be used to examine categorical variables by assessing frequencies. Missing data will be reported for each variable.

3.1.2.2 Approach to missing data.

Based on the descriptive analyses, the most appropriate strategy for accounting for missing data will be chosen. Although this approach does not provide definitive information, the level of missingness and the informativeness of the missing data (i.e., missing completely at random, missing at random, missing not at random) will be assessed by using graphical representation and a statistical assessment to determine if participants with missing data differ appreciably from those without missing data. When appropriate, inverse probability weighting will be used to account for missing data. Sensitivity analyses will be used to evaluate if the results obtained with the inverse probability weighting strategy differ appreciably from the results obtained with a listwise deletion strategy.

3.1.2.3 Main analyses.

An "intent-to-treat" analysis will be used to test the study hypotheses. The primary outcomes of interest will be 1) the change in knowledge about human rights and 2) the change in attitudes of mental health professionals towards people with psychosocial disabilities and their role as right-holders.

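### The stated 126 per arm is larger than the protocol's own inputs require, and the primary effect is not pinned down: two primary outcomes, three follow-up visits, no primary visit, no success rule

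*Protocol*

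**What the plan says.** Section 3.2.1.14 sets a "two-sided alpha level of 0.05 and power of 0.80" and bases the calculation on "the ability to detect an effect size of 0.5 standard units at the total score" of the attitudes questionnaire. It continues: "The 28 hospitals unit clusters will be randomized with a 1:1 allocation ratio to the intervention or control arm"; "we assume a 20% loss to follow-up and ICC=0.05"; and, from these, "we calculated that 126 participants would be required in each arm group". It gives no cluster size and no formula, and it does not say which visit the 0.5 refers to.

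Section 3.1.2.3 states: "The primary outcomes of interest will be 1) the change in knowledge about human rights and 2) the change in attitudes". It then says "Each outcome will be analyzed separately using LME", with the arm-by-time interaction as the intervention effect and time as a categorical variable covering post-training, 3 months and 6 months. Results are promised in this form: "Effect sizes will be reported as mean differences for each time point and intervention arm, with 95% confidence intervals". The equation printed below that text has one coefficient for time and one for the interaction, with time coded 0, 1, 2, 3.

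The primary hypothesis in section 1 (Specific aims) joins better knowledge and improved attitudes with 'and', but no decision rule follows from it anywhere.

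**The concern.** There are two separate problems.

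- **The sample size cannot be traced.** It is presented as the number needed for 80% power, but the listed inputs lead to a smaller number. A reader cannot tell what power the trial has.
- **The primary effect is not identified.** The protocol could be read as one slope per outcome (the equation), one joint interaction test per outcome, or three visit contrasts per outcome (the categorical text and the per-visit intervals). Nothing says which result decides the trial, or whether one positive outcome is enough. The only alpha in the document, 0.05, was set for one comparison of one outcome. If the visit and the outcome can be settled after the data are seen, neither that error rate nor the stated power belongs to the claim eventually made. Section 2.6 says the Ghanaian authorities want this efficacy result before scaling up nationally, so the claim will be used.

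**Working it through.** **Sample size.** Inputs, all from section 3.2.1.14: d = 0.5; two-sided alpha 0.05; power 0.80; ICC 0.05; 28 units at 1:1, so 14 per arm; 20% loss.

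Without clustering: n = 2(1.96 + 0.842)² / 0.5² = 62.8, so 63 per arm.

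Adding clustering and loss by the usual routes:

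- Fixed 14 units per arm, normal: 63 × 14 × 0.95 / (14 − 63 × 0.05) = 77.2 completers; 77.2 / 0.8 = 96.5, so **97** (98 at 7 per unit).
- Design effect at 7.2 completers per unit: 1 + 6.2 × 0.05 = 1.31; 62.8 × 1.31 = 82.3; / 0.8 = **103**.
- Noncentral t with 26 df (28 units − 2): about **107**.
- Design effect at 9 per unit: 1 + 8 × 0.05 = 1.40; 63 × 1.40 = 88.2; / 0.8 = 110.25, so **111** (**112** starting from a t-based 64).

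So the stated inputs need about 97-112, and 126 is 12% (126/112) to 30% (126/97) larger. A design effect of 1.6 does return it exactly: 63 × 1.6 / 0.8 = 126. But that implies 13 per unit, and 28 × 13 = 364, whereas 2 × 126 = 252, an average of 9 per unit.

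Power that 126 delivers: 126 × 0.8 = 100.8 completers per arm, or 7.2 per unit; effective n = 100.8 / 1.31 = 76.9; standard error √(2/76.9) = 0.161; 0.5 / 0.161 = 3.10.

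| Recruited per arm | Normal, 0.05 | t 26 df, 0.05 | Normal, 0.025 | t 26 df, 0.025 |
|---|---|---|---|---|
| 98 | 0.81 | 0.78 | 0.72 | 0.67 |
| 112 | 0.84 | 0.82 | 0.77 | 0.72 |
| 126 | 0.87 | 0.85 | 0.80 | 0.76 |

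**Error rate.** The protocol gives no correlations between visits or outcomes, so those below are assumptions. Simulated figures use 400,000 multivariate normal draws per setting, each test two-sided at 0.05.

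- *Either outcome suffices, one test each:* 1 − 0.95² = 9.75% if independent; 9.1% at outcome correlation 0.5.
- *Either outcome suffices, each visit tested:* 1 − 0.95⁶ = 26.5% if all six are independent; 19-23% for visit correlation 0.5-0.7 and outcome correlation 0-0.5; 16% at visit correlation 0.8 and outcome correlation 0.7. These count both directions. False claims of benefit are about half: roughly 10-12% in the 0.5-0.7 settings, against a nominal 2.5% for one test.
- *Both outcomes must succeed, one test each:* at most 5%.
- *Both must succeed, visit left open, one outcome truly improved:* the error on the null outcome is that of three correlated tests, 12.5% at visit correlation 0.5, 11% at 0.7 and 10% at 0.8.

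**The case against.** The strongest reply is that the protocol never says six tests will be run. The per-visit sentence is about reporting effect sizes. The 0.05 appears only in the sample size section, and the printed equation has one interaction coefficient, hence one test per outcome. The hypothesis joins the outcomes with 'and', and if both must succeed on one test each, error is held at 5%. All of this stands. A reader might infer that every visit is tested at 0.05 and that the false-claim rate is therefore about 20%. The document does not support that: it needs separate visit tests, an any-one-wins rule and correlations the protocol does not give, and it counts results in both directions.

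It can also be said that multiplicity rules are commonly left to a statistical analysis plan. That is fair for the choice between, say, Holm and Bonferroni. It does not answer the conflict between text and equation, which lies in what the protocol itself fixes, and requiring both outcomes does not help while the visit is open.

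On sample size, the objection is that the discrepancy is harmless in direction. It is. A reader might infer from a figure that does not reproduce that the trial is underpowered; for its stated target it is not. What remains is a figure described as required that the stated inputs do not require.

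**Conclusion.** Both points hold, within limits.

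- **Sample size:** 126 per arm is not what the stated inputs require (about 97-112, depending on method). It is conservative, giving 85% (t, 26 df) to 87% (normal) power for one outcome at one visit at two-sided 0.05. This assumes equal unit sizes, averaging 9 recruited per unit; that average comes from division and is not stated in the protocol.
- **Primary effect:** it is undetermined, because text and equation disagree and no visit or success rule is given. Error ranges from at most 5% (both required, one test each), through 9-10% (either suffices, one test each), to roughly 16-26% (either suffices, every visit tested). The last range rests wholly on assumed correlations and on a testing scheme the protocol does not state, so it is an outer case and not the trial's error rate.

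This should be corrected, but neither point undermines the design.

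**What to change.** **Section 3.1.2.3**

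- Name one primary visit for both outcomes. Either 3 or 6 months would be consistent with the protocol's criticism of short-term-only evidence and its call for at least three months of follow-up; the choice is the sponsor's.
- Make the arm-by-time contrast at that visit the primary effect. Rewrite the equation with indicator terms for each post-baseline visit and one interaction term per visit, so that it matches categorical time.
- State the success rule: either test the two outcomes at that visit by Holm at overall two-sided 0.05, or require both, each at 0.05. Treat the other visits as secondary.

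**Section 3.2.1.14**

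- Show the cluster size and formula, and replace the claim that 126 is required with the power it gives: about 85-87% at 0.05, and 76-80% at 0.025 per outcome.

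**Cost.** Wording only, with no change in enrolment. Under Holm, first-step power per outcome is about 76-80%, possibly just below the 80% target; on the t calculation about 144 per arm would restore it. If both outcomes must succeed, the chance of winning both is below the single-outcome figure: 0.85² = 0.72 to 0.87² = 0.76 if the outcomes were independent, and higher if they are positively correlated. These figures assume that knowledge has the same 0.5 effect and ICC as attitudes, which the protocol does not say.

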- The **Seclusion and Restraint Experience Questionnaire (SREQ)** [Appendix 9] [181] (44 items) was developed to measure emotional and ethical experiences linked to the use of seclusion and restraint among nurses. In this study, an abbreviated version of the scale (25 items), modified for the use among mental health providers, will be used to address seven domains: Negative Experiences, Positive Experiences, Experiences of Control, Experiences of Duty, Experiences of the Misuse of Seclusion and Restraint, Experiences of Seclusion and Restraint as Good Mental Health Practice, Experiences of Ethical Challenge.

The following data will also be collected:

- Information on the enrollment in the online WHO QualityRights training;
- Information on the enrollment in other potential interventions;
- Information on potential contacts with mental health professionals working in other units;
- Information on participants' satisfaction with the course.

The psychometric properties of the WHO's Knowledge about the Rights of persons with psychosocial disabilities questionnaire, the WHO's questionnaire on the attitudes towards people with psychosocial disabilities as rights-holders, and the Practices related to substitute-decision making and coercion scale (the questionnaire I plan to use in Aim 2) have not been tested in Ghana. A description of how we plan to evaluate these instruments' psychometric properties will be made in a separate document.

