Appendix 5. Schedule of enrollment, intervention, and assessments

	Recruitment	Pre-Intervention	Post-intervention	Follow-up (3 months)	Follow-up (6 months)
Eligibility criteria	x				
Informed consent	x		x	x	x
Allocation		x			
Socio-demographic questionnaires		x			
WHO's Knowledge about the rights of persons with psychosocial disabilities questionnaire		x	x	x	x
WHO's questionnaire on the attitudes towards people with psychosocial		x	x	x	x

disabilities as rights-holders					
Practices related to substitute-decision making and coercion scale		x		x	x
Abbreviated SREQ		x	x		
Information on the enrollment in the online WHO QualityRights training		x	x	x	
Information on the enrollment in other potential interventions		x	x	x	
Information on contacts with mental health professionals working in units allocated to a different arm		x	x	x	
Information on the satisfaction about the training			x		

Appendix 6. World Health Organization's Knowledge about the Rights of persons with psychosocial disabilities questionnaire

Please indicate if the following statements are True (T) or False (F).

		T	F
1	All 30 human rights within the Universal Declaration of Human Rights (UDHR) are needed to live a good life.		
2	The Universal Declaration of Human Rights (UDHR) is a law.		
3	Human rights can never be restricted.		
4	Violations of human rights can only be carried out by individuals, not by governments.		
5	The Convention on the Rights of People with Disabilities (CRPD) is a convention that protects the rights of all marginalized groups.		
6	According to the CRPD, people with dementia have the right to live in the community and to choose their living arrangements		
7	Informed consent is when a person's family members receive information about		

	different possible treatment options in order to make an informed decision.		
8	Advance plans/directives are documents made by health practitioners to plan in advance the treatment of people using the service.		
9	To promote legal capacity, family members, caregivers, and supporters should help people make decisions by explaining different options but should not assist in communicating decisions to others.		
10			
	Was intended to create new rights for people with disabilities		
	Adopts the medical and charity models of disability		
	Adopts the social and human rights models of disability		
	Is binding on countries which have ratified it		
11			
	Must show their ability to understand rights in order to claim them		

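### Change in seclusion and restraint experiences is to be analysed at three and six months, but the schedule gives the SREQ only before and right after training

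*Protocol*

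**What the plan says.** Section 3.1.2.4 of the protocol sets the analysis times for the two secondary outcomes in one sentence. For practices: "The change in practices will be evaluated at three months and six months". For experiences: "the change in experiences will be evaluated both post-intervention and at three months and six months". On method it adds: "These changes will be evaluated using the same methodology already described for the main analyses".

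That method, in section 3.1.2.3, is a linear mixed model with arm, time and their interaction. On time it says: "Time will be entered as a categorical variable with levels corresponding to post-training and 3 AND 6 months". The key to the model equation codes baseline as 0 and the three later occasions as 1 to 3.

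Section 3.2.1.10 names the instrument for experiences. It is the SREQ, of which "an abbreviated version of the scale (25 items), modified for the use among mental health providers, will be used".

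Section 3.1.1.9 refers to Appendix 5 for the schedule of enrollment and assessment. In Appendix 5 the row "Abbreviated SREQ" is marked at pre-intervention and post-intervention only. Nothing else in the protocol schedules the SREQ later. Section 3.1.1.5 mentions questionnaires at three and six months but does not say which ones.

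**The concern.** The analysis text needs the SREQ on four occasions and the schedule provides two. Anyone programming the online assessments from Appendix 5 would leave the SREQ out at three and six months, and the gap might not be noticed until analysis.

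What would be lost is the evidence on whether any change in experiences lasts. Change in practices and experiences is the stated secondary aim. Section 2.4 criticises earlier studies for measuring only short-term effects, and section 2.5 asks for repeated measures with at least three months of follow-up. Under Appendix 5 the trial would repeat that weakness for this outcome.

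The loss would be permanent. The inverse probability weighting and listwise deletion in section 3.1.2.2 both need some participants observed at a visit. Neither helps when the outcome is absent for everyone.

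**Working it through.** **Step 1. Compare analysis times with scheduled times.** Analysis times come from sections 3.1.2.3 and 3.1.2.4, scheduled times from Appendix 5. Change from baseline also needs a baseline measure.

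| Instrument | Times the analysis needs | Times marked in Appendix 5 | Agree? |
|---|---|---|---|
| Knowledge | baseline, post, 3 m, 6 m | baseline, post, 3 m, 6 m | yes |
| Attitudes | baseline, post, 3 m, 6 m | baseline, post, 3 m, 6 m | yes |
| Practices | baseline, 3 m, 6 m | baseline, 3 m, 6 m | yes |
| Abbreviated SREQ | baseline, post, 3 m, 6 m | baseline, post | **no** |

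**Step 2. Rule out a column shift.** The table is broken in the text version, so a displaced mark is possible in principle. The row "Practices related to substitute-decision making and coercion scale" sits directly above the SREQ row. It has an empty post-intervention cell between filled ones, and this matches section 3.1.2.4 exactly. The columns are therefore aligned there. The SREQ row also has only two marks in total, so no shift could produce the four that are needed.

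**Step 3. Rule out loose wording.** Section 3.1.2.4 contrasts the two secondary outcomes: practices at two times, experiences at those two plus post-intervention. The times were distinguished on purpose.

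**Step 4. Effect on the model.** With four occasions the arm-by-time interaction gives three contrasts against baseline: post, three months and six months. With two occasions it gives one. Contrasts without data: 3 − 1 = 2 of 3. The autoregressive covariance reduces to a single correlation between two measurements.

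**Step 5. The sample size behind the volume figure.** Section 3.2.1.14 gives 126 per arm, from "two-sided alpha level of 0.05 and power of 0.80", a difference of 0.5 SD, an ICC of 0.05, 20% loss and 28 units (k = 14 per arm). The figure can be reproduced with t quantiles on 28 − 2 = 26 degrees of freedom:

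- Unclustered n per arm = 2 × ((t₀.₉₇₅ + t₀.₈₀) / 0.5)² = 67.8
- Participants per unit m = n(1 − ICC) / (k − n × ICC) = 67.8 × 0.95 / (14 − 67.8 × 0.05) = 6.07, rounded up to 7
- Allowing for loss: 7 / 0.8 = 8.75, rounded up to 9
- Per arm: 9 × 14 = 126

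The calculation is based on the attitudes score, so the SREQ discrepancy does not affect it.

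**Step 6. Volume of data not collected.**

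- Participants: 126 × 2 = 252
- Questionnaires over two visits: 252 × 2 = 504
- With 20% loss taken to apply at both visits: 504 × 0.8 = 403.2, about 403

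**The case against.** The discrepancy itself is hard to dispute; the case on the other side concerns its weight and the remedy.

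- **The outcome is not wholly lost.** The post-intervention SREQ is scheduled, so one of the three contrasts is fully supported and the arm-by-time interaction can still be estimated for it. This stands. The gap is confined to three and six months, which are the visits Appendix 5 itself labels as follow-up.
- **Only a secondary outcome is affected.** This also stands. Knowledge and attitudes are scheduled at all four times, practices at every time its analysis needs, and power is untouched.
- **Appendix 5 may simply be out of date.** The rows for QualityRights enrollment, other interventions and contacts across arms stop at three months, although section 3.1.1.6 wants the enrollment information at every assessment. A six-month visit added late would explain those rows. It does not fully explain the SREQ row, which lacks three months as well. A clerical cause would not make the schedule any safer to follow.
- **The loss is conditional.** It occurs only if data collection follows Appendix 5 rather than section 3.1.2.4, and the protocol does not say which governs. This is true. But Appendix 5 is the only place that allocates instruments to visits.
- **The two texts could be reconciled the other way,** by limiting the analysis to post-intervention. That is possible, and the protocol does not prove which was meant. The explicit times in section 3.1.2.4 and the stated interest in longer-term effects point towards collecting the data.

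**Conclusion.** The concern holds. Section 3.1.2.4 and Appendix 5 contradict each other on when the SREQ is given. Following Appendix 5 would leave two of the three planned contrasts for experiences with no observations: up to 504 questionnaires, or about 403 with the assumed loss.

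The count of contrasts rests only on reading the two places together. The questionnaire totals assume full recruitment of 126 per arm and, for the lower figure, 20% loss at both visits. They show the amount of data at stake, not an effect on any conclusion.

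The primary hypothesis and the sample size are not affected. It still must be put right before the follow-up assessments begin, because missed data cannot be collected afterwards and the correction beforehand is cheap.

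**What to change.** In Appendix 5, mark the abbreviated SREQ at three months and at six months, and include it in the online questionnaires for those two visits, so that collection matches section 3.1.2.4.

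The cost is a schedule correction and 25 short items on each of two online assessments that participants already complete, with slightly more respondent burden.

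If the investigators in fact meant to measure experiences only immediately after training, section 3.1.2.4 should be amended to say so. That also removes the contradiction, but gives up the evidence on durability for this outcome.
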